### **Statistical methods**

For Cohort 1, with a total sample size of 24 participants we can detect an absolute difference of 10% change from baseline in glucose AUC(0-4) (mmol/L 4h), ie, a difference of ~134 mmol/L 4h between prednisolone and AZD9567, with a power of 80% and significance level of 0.05, 1-sided test. Withdrawn participants should be replaced to ensure that 24 participants are evaluable (12 in each sequence group).

The primary PD variable, change from baseline in glucose AUC(0-4) following a standardised MMTT, will be analysed using a linear mixed model with baseline included as covariate. Treatment, period and sequence will be included as fixed effects with participant within sequence as random effect. Models will be run separately for each cohort. Should there be more than 10% of participants erroneously treated, a sensitivity analysis will be performed using the actual treatment received instead. Descriptive statistics and graphical presentations will be presented.

Mean daily glucose measured by continuous glucose monitoring (CGM) is a secondary endpoint and will be analysed using a MMRM analysis with baseline as covariate. Treatment, period and sequence will be included as fixed effects, participant within sequence as random effect and day as repeated measure. Models will be run separately for each cohort. Similar analyses will be performed for the rise in mean daily glucose over 24-hour periods. Fasting glucose as derived from the baseline measure in the MMTT, change in hormones related to glucose homeostasis in response to MMTT (insulin, glucagon, GLP-1, glucose-dependent insulin releasing polypeptide [GIP]), changes in FFAs during MMTT, HOMA-IR, HOMA-S, and 24-hour U-Na and U-K excretion and the ratio between them will be analysed in a similar way to the primary PD endpoint.

Safety will be assessed by descriptive analysis of adverse events (AEs)/serious AEs (SAEs), vital signs, ECGs, clinical laboratory assessments (clinical chemistry/haematology), morning serum cortisol, and adrenocorticotrophic hormone (ACTH).

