### **9.4.2.2 Secondary Endpoint(s)**

Mean daily glucose as measured by CGM will be evaluated as a secondary endpoint.

The mean daily glucose will be analysed using an MMRM analysis with baseline as covariate. Treatment, period, and sequence will be included as fixed effects, participant within sequence as random effect, and day as repeated measure. Models will be run separately for each cohort.

Similar analyses will be performed for the rise in mean daily glucose over 24-hour periods.

The secondary endpoints (insulin, glucagon, GLP-1, GIP), changes in FFAs during MMTT, C-peptide, 24-hour U-Na and U-K excretion and the ratio between them,  $\Delta I_{10}/\Delta G_{10}$ ,  $\Delta I_{30}/\Delta G_{30}$ ,  $\Delta C_{10}/\Delta G_{10}$ ,  $\Delta C_{30}/\Delta G_{30}$  and C-peptide will be summarised and analysed by means of a linear model or a mixed model for repeated measurements.

LPS-stimulated whole blood TNF $\alpha$  levels will be evaluated as a secondary endpoint for participants in Cohort 1 and Cohort 2 (high and low dose comparison). For TNF $\alpha$  profiles, the AUC will be estimated and the measurements at the sampling points will be summarised. Descriptive statistics will be tabulated both for the AUC and individual measurement points and treatments comparison will be conducted with ANOVA. Models will be run separately for each cohort.

Further details on statistical analyses will be provided in the SAP.

Descriptive statistics and graphical presentations will be presented as appropriate.

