2 OBJECTIVES AND ENDPOINTS

Objectives	Endpoints/Outcome measures
Primary	
To determine the PD effect of AZD9567 on glucose homeostasis compared to prednisolone	
 • Primary endpoint: Change in glucose AUC(0-4) versus baseline compared to prednisolone following a standardised MMTT
Secondary	
To determine the effect of AZD9567 on CGM compared to prednisolone	
 • Mean daily glucose at 48 – 72 hours treatment as determined from multiple measures via the CGM system • Rise in mean daily glucose over 24-hour periods from start of IMP dosing (0 – 24 hours, 24 – 48 hours, 48 – 72 hours)
To determine the PD effect of AZD9567 following a MMTT compared to prednisolone	
 • Change from baseline in fasting glucose • Change from baseline AUC(0-4) on hormones related to glucose homeostasis (insulin, glucagon, GLP-1, GIP) and FFAs

Objectives	Endpoints/Outcome measures
To determine the PD effect of AZD9567 on glucose homeostasis through an MMTT in comparison to prednisolone	
 • Change from baseline in AUC(0-4) on insulin and C-peptide
To determine the PD effect of AZD9567 on derived measures of beta cell function from the MMTT compared to prednisolone	
 • MMTT derived first phase insulin response ($\Delta I_{10}/\Delta G_{10}$, $\Delta I_{30}/\Delta G_{30}$, $\Delta C_{10}/\Delta G_{10}$, $\Delta C_{30}/\Delta G_{30}$ - - where, Δ: change from baseline, I: insulin, C: C-peptide, G: glucose) • Homeostatic model assessment of insulin resistance (HOMA-IR), homeostatic model assessment of insulin sensitivity (HOMA-S)
To determine the effect of AZD9567 on U-Na and U-K excretion compared to prednisolone	
 • 24-hour sodium and potassium concentration
To evaluate the PK of AZD9567 following once daily dosing	
 • Plasma PK parameters
To collect plasma samples for analysis of prednisolone. Reported outside the CSR	
 • Plasma concentrations of prednisolone
To explore the relationship between AZD9567 exposure and inhibition of LPS-stimulated TNF α release for high and low dose comparison (Cohort 1 and Cohort 2)	
 • TNFα concentrations
Safety	

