The same steps i) to iii) accordingly to timepoints 10 and 30, will be performed for $\Delta C_{10} / \Delta G_{10}$, $\Delta I_{30} / \Delta G_{30}$, and $\Delta C_{30} / \Delta G_{30}$.

The comparison of the effect of the two treatments on the change in $\Delta I_{10} / \Delta G_{10}$ and $\Delta I_{30} / \Delta G_{30}$, between Days -1 and 4 will be performed by the same model as that for the comparison of the primary endpoint.

The following comparison will be performed for the change from baseline and the percent change from changes from baseline at Day 4 at 10 and 30 minutes:

- 72 mg AZD9567 versus 40 mg prednisolone (Cohort 1)
- 40 mg AZD9567 versus 20 mg prednisolone (Cohort 2)
- placebo versus 5 mg prednisolone (Cohort 3).

The previous analyses will be repeated for the comparison of the effect of the two treatments on the change in $\Delta C_{10} / \Delta G_{10}$, $\Delta C_{30} / \Delta G_{30}$ using C-peptide instead of insulin in the calculation of these ratios.

HOMA-IR and HOMA-S

A summary of the baseline HOMA-IR and HOMA-S and at Day 4 as well as change from baseline, will be provided by treatment.

24-hour U-Na and U-K

The 24-hour Na and K concentration and its ratio (Na/K) in urine will be analysed as the primary endpoint.

The following comparisons will be performed for the change and percentage change from baseline at 0-24 hours on Day 3:

- 72 mg AZD9567 versus 40 mg prednisolone (Cohort 1)
- 40 mg AZD9567 versus 20 mg prednisolone (Cohort 2)
- placebo versus 5 mg prednisolone (Cohort 3).

TNF α concentrations

Descriptive statistics will be tabulated for the individual measurement points of the LPS-stimulated TNF α levels.

An ANOVA model with treatment, sequence and subject as random effect will be run separately for each cohort (Cohort 1 and Cohort 2) for the comparisons of the treatments at Day 3.

A scatter plot of individual plasma concentrations of AZD9567 (nmol/L) in a log scale on the X axis versus individual LPS-Stimulated TNF α Levels (ng/L) in log scale on the Y axis will be created.

CCI

[Redacted content]

CCI

CONFIDENTIAL

Project Document Version No. Final 2.0

Project Document Effective Date: <Date of last signature>

CCI [REDACTED]

[REDACTED]

[REDACTED]

[REDACTED]

[REDACTED]

[REDACTED]

[REDACTED]

[REDACTED]

Calculations of endpoints analysed by statistical models

Calculation of changes from baseline AUC (0-4)

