$$\text{HOMA - IR} = \frac{\text{Glucose} \left(\frac{\text{mmol}}{\text{L}} \right) \times \text{Insulin (mU/L)}}{22.5}$$

HOMA-S will be calculated as the reciprocal of HOMA-IR.

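### HOMA-IR and HOMA-S get no modelled comparison with prednisolone in the SAP, although the protocol synopsis promises one

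*SAP*

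**What the plan says.** SAP section 2 lists HOMA-IR and HOMA-S as secondary endpoints under this objective: "To determine the PD effect of AZD9567 on derived measures of beta cell function from the MMTT compared to prednisolone". The protocol synopsis and Protocol section 3 carry the same objective. Its other endpoint group is the "MMTT derived first phase insulin response" (insulin or C-peptide over glucose at 10 and 30 minutes).

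The documents give three accounts of the HOMA analysis:

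- The protocol synopsis, under statistical methods, commits to a model: "HOMA-IR, HOMA-S, and 24-hour U-Na and U-K excretion and the ratio between them will be analysed in a similar way to the primary PD endpoint".
- Protocol 9.4.2.2 names a set of secondary endpoints that "will be summarised and analysed by means of a linear model or a mixed model for repeated measurements". HOMA-IR and HOMA-S are not named there.
- SAP 4.12.2 gives one sentence: "A summary of the baseline HOMA-IR and HOMA-S and at Day 4 as well as change from baseline, will be provided by treatment". None of the three cohort comparisons listed for neighbouring endpoints follows it.

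The SAP derives HOMA-IR from the pre-meal glucose and insulin of the MMTT and adds: "HOMA-S will be calculated as the reciprocal of HOMA-IR". That derivation sits in the part of 4.12.2 whose subheading announces calculations for endpoints that are analysed by model. SAP 4.15, which records departures from the protocol's methods, lists only the time term added to the repeated-measures model.

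**The concern.** Following the SAP as written produces no estimated treatment difference and no interval for two secondary endpoints whose objective is comparative. The protocol names insulin resistance as one way glucocorticoids disturb glucose control, and in the unredacted text HOMA is the only secondary endpoint labelled as measuring it. Fasting glucose, one of its two inputs, gets a modelled contrast. Fasting insulin, the other, does not: insulin is compared as AUC(0-4) and as post-meal increments.

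Summaries by treatment also set aside two features of a cross-over, the pairing within participants and the adjustment for period. And because the texts disagree, the choice between a model and a description stays open until results are seen.

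**Working it through.** The plan gives no figure for HOMA, so there is nothing to reproduce. The check compares the texts and then asks what the planned tables would let a reader recover.

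**Step 1. The texts side by side**

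| Place | HOMA-IR, HOMA-S | Neighbouring endpoints |
|---|---|---|
| Objectives (both documents) | Secondary, compared with prednisolone | First-phase ratios under the same objective |
| Protocol synopsis | Like the primary endpoint | Fasting glucose, hormones, FFAs, urinary Na and K in the same sentence |
| Protocol 9.4.2.2 | Not named | Hormones, FFAs, C-peptide, urinary Na and K, first-phase ratios named; fasting glucose not named |
| SAP 4.12.2 | Summary by treatment only | Fasting glucose, AUC(0-4) endpoints, first-phase ratios, urinary Na and K all use the primary-endpoint model |
| SAP 4.15 | No change declared | Time term only |

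Among the MMTT-derived secondary endpoints, HOMA alone has no contrast.

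**Step 2. What the summaries give**

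Let d be a participant's change on AZD9567 minus the change on prednisolone. If all n participants complete both periods, the difference between the two mean changes equals the mean of d, so the point estimate is recoverable. Its variance is (s_A² + s_P² − 2·r·s_A·s_P)/n. The tables supply s_A and s_P but not r, the correlation between the two change scores.

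With equal SDs, an unpaired reading gives a standard error 1/√(1 − r) times the paired one. The relevant r is between changes, not between levels, because each period has its own Day -1 baseline. Suppose the four measurements (Day -1 and Day 4 in two periods) share variance σ² and a common correlation ρ. The covariance of the two changes is then σ²(ρ − ρ − ρ + ρ) = 0, so r = 0 and the ratio is 1 whatever ρ is. A response shared across both drugs would make r positive. The documents give no value.

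Two further limits apply. The full analysis set needs only one dose, so a participant with one period enters only one treatment's mean. And with unequal sequence groups, a period effect enters the unadjusted difference.

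**Step 3. The reciprocal**

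Invented values show that arithmetic means of HOMA-IR and HOMA-S can disagree. Take HOMA-IR of 2 and 8 on one treatment, and 4 and 5.9 on the other.

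- Mean HOMA-IR: (2 + 8)/2 = 5.00 against (4 + 5.9)/2 = 4.95, so the second looks less resistant.
- Mean HOMA-S: (0.500 + 0.125)/2 = 0.313 against (0.250 + 0.169)/2 = 0.210, so the second looks less sensitive.

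On the log scale, log HOMA-S = −log HOMA-IR. Outcome and baseline both change sign, so the treatment estimate changes sign and its standard error is unchanged.

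**Step 4. What a modelled contrast would deliver**

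For a two-sequence cross-over, the 95% CI half-width is about t(0.975, n − 2)/√n times the SD of the within-participant difference:

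- Cohort 1, n = 24: 2.074/4.899 = 0.42 SD.
- Cohorts 2 and 3, n = 8 each: 2.447/2.828 = 0.87 SD.

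No SD for HOMA is given, so these cannot be put in HOMA units.

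**The case against.** The strongest reply is that the SAP follows the protocol body. Section 9.4.2.2 does not list HOMA among the modelled endpoints, and Amendment 2 revised the analysis text of that section. Measured against it, the SAP has no clear departure to declare. This stands in part: the conflict lies within the protocol as well as between protocol and SAP. It does not show that a descriptive analysis was intended, because 9.4.2.2 also omits fasting glucose, which the SAP still models.

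Three stronger readings are tempting, and the documents do not support them:

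- A reader might infer that the whole objective goes without a contrast. The four first-phase ratios get the primary-endpoint model in all three cohorts.
- A reader might infer that the comparison cannot be made at all. With complete pairs, direction and size can be read from the mean changes, and Protocol 9.4.1 appends raw data listings to the study report. What is missing is a planned interval and period adjustment.
- A reader might attach a standard-error inflation factor by assuming a high within-participant correlation. That correlation would be of levels, whereas the SAP summarises changes, whose correlation is not given and could be near zero.

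The reciprocal argument also has a limit. The SAP's summaries include medians and quartiles, which for levels largely agree in direction between HOMA-IR and HOMA-S. The disagreement in means is a possibility, not an expected result.

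**Conclusion.** The concern holds for the HOMA endpoints only. They are comparative secondary endpoints, the synopsis commits them to a primary-type analysis, and the SAP plans no treatment difference, interval or period adjustment for them. Protocol 9.4.2.2 agrees with neither text clearly, and SAP 4.15 is silent.

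The conclusion rests on the wording alone and needs no assumed correlation or SD, because no contrast is planned whatever their values. Its weight is moderate: these are secondary endpoints in a Phase 2a study without multiplicity adjustment, Cohorts 2 and 3 are exploratory, and the primary analysis is untouched. It should still be corrected, because the model is already specified and the data are already derived.

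**What to change.** In SAP 4.12.2, analyse HOMA-IR in each cohort with the log-scale version of the primary-endpoint mixed model. The outcome is log Day 4 minus log Day -1, with log Day -1 as covariate, treatment, period and sequence as fixed effects, and participant within sequence as random effect. Report the geometric mean ratio with its 95% CI for the three cohort comparisons, and keep the planned summaries.

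The log version is preferable because HOMA-IR is positive and HOMA-S is its reciprocal. One fit then covers both endpoints, and they cannot disagree in direction. Show the ratio itself beside the SAP's percentage format, since percentages do not mirror each other: a HOMA-IR ratio of 0.80 (−20%) is a HOMA-S ratio of 1/0.80 = 1.25 (+25%).

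Add HOMA-IR and HOMA-S to the modelled list in Protocol 9.4.2.2 so that the synopsis, that section and SAP 4.12.2 agree. If the sponsor prefers HOMA to be descriptive, the synopsis should say so and SAP 4.15 should declare it, at the price of leaving this part of the objective without an interval.

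Cost: one extra model per cohort and a short text alignment. No new data are needed.

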### 3 OBJECTIVES AND ENDPOINTS

**Table 2 Objectives and Endpoints**

Objectives	Endpoints/Outcome measures
Primary	
To determine the PD effect of AZD9567 on glucose homeostasis compared to prednisolone	
 
• Primary endpoint: Change in glucose AUC(0-4) versus baseline compared to prednisolone following a standardised MMTT
 

Secondary	
To determine the effect of AZD9567 on CGM compared to prednisolone	
 
• Mean daily glucose at 48 – 72 hours treatment as determined from multiple measures via the CGM system
 
• Rise in mean daily glucose over 24-hour periods from start of IMP dosing (0 – 24 hours, 24 – 48 hours, 48 – 72 hours)
 

To determine the PD effect of AZD9567 following a MMTT compared to prednisolone	
 
• Change from baseline in fasting glucose
 
• Change from baseline AUC(0-4) on hormones related to glucose homeostasis (insulin, glucagon, GLP-1, GIP) and FFAs
 

To determine the PD effect of AZD9567 on glucose homeostasis through an MMTT in comparison to prednisolone	
 
• Change from baseline in AUC(0-4) on insulin and C-peptide
 

To determine the PD effect of AZD9567 on derived measures of beta cell function from the MMTT compared to prednisolone	
 
• MMTT derived first phase insulin response (<math>\Delta I_{10}/\Delta G_{10}</math>, <math>\Delta I_{30}/\Delta G_{30}</math>, <math>\Delta C_{10}/\Delta G_{10}</math>, <math>\Delta C_{30}/\Delta G_{30}</math> – where, <math>\Delta</math>: change from baseline, I: insulin, C: C-peptide, G: glucose)
 
• Homeostatic model assessment of insulin resistance (HOMA-IR), homeostatic model assessment of insulin sensitivity (HOMA-S)
 

To determine the effect of AZD9567 on U-Na and U-K excretion compared to prednisolone	
 
• 24-hour sodium and potassium concentration
 

To evaluate the PK of AZD9567 following once daily dosing	
 
• Plasma PK parameters
 

Objectives	Endpoints/Outcome measures
To collect plasma samples for analysis of prednisolone. Reported outside the CSR	
 
Plasma concentrations of prednisolone
 

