### **8.2.3 24-hour Urinary Sodium (U-Na) and Urinary Potassium (U-K)**

On Days -1 and 3 and Days 27 and 30, the concentration of sodium and potassium in urine will be measured over 24 hours.

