3.2.1 Pharmacodynamic Variables

Continuous Glucose Monitoring (CGM)/Flash Glucose Monitoring (FGM)

A CGM/FGM device will be fitted on an Out-patient' basis on Day -4 and removed on Day 4. Mean daily glucose will be determined from multiple measures.

Mixed Meal Tolerance Test (MMTT)

On Days -1 and 4, a standardised mixed meal (meal should be consumed as fast as the participant can, within 30 minutes) will be administered around 07:00 a.m., after an overnight fast of 12 hours. Blood samples will be taken according to the schedule in section 6.2 for analysis of glucose, insulin, C-peptide, Glucagon-like peptide-1 (GLP-1), Glucose-dependent insulin releasing polypeptide (GIP), glucagon and free fatty acids (FFAs).

24-hour Urinary Sodium (U-Na) and Urinary Potassium (U-K)

On Days -1 and 3, sodium and potassium concentrations in urine will be measured over 24 hours.

TNF α Concentrations

On Day 3, TNF α concentrations in blood will be measured and analysed with and without stimulation with LPS in Cohorts 1 and 2.

CCI [Redacted]

[Redacted]

[Redacted]

[Redacted]

[Redacted]

[Redacted]

CCI [Redacted]

[Redacted]

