4.8 Baseline, change from baseline and percentage change from baseline definitions

Demography and baseline characteristics

For demography and baseline characteristics other than weight, the baseline will be the assessment at screening. For weight, the baseline will be the assessment at Day -1 performed by means of the **CCI** device. If the weight at Day -1 is missing, the weight at Day -2 (or at Screening, in the case of period 1 if the value at Day -2 is also missing) will be the baseline for such a period.

Pharmacodynamics

Change in AUC(0-4)

In the case of the linear mixed models for the change from baseline in glucose AUC(0-4) (primary endpoint), hormones related to glucose homeostasis (insulin, glucagon, GLP-1, GIP), FFAs and C-peptide (secondary endpoints), the baseline measurement will be the AUC(0-4) on Day -1 (i.e., prior to first dosing) of each period.

Glucose concentrations assessed by CGM

For the calculation of the rise in mean glucose and the mean daily glucose, the baseline will be the average of the values from -24 hours to first dosing on Day 1 (values from -72 to -24 hours will be excluded from the baseline) of each period.

For the MMRM for the rise in mean glucose and the mean glucose, the baseline included as a covariate in the model will be the value -24 hours to first dosing on Day 1 of each period.

MMTT derived first phase insulin response

For the calculation of the change from baseline of insulin, glucose and C-peptide included in the calculation of $\Delta I10/\Delta G10$, $\Delta I30/\Delta G30$, $\Delta C10/\Delta G10$ and $\Delta C30/\Delta G30$, the baseline will be value at Day -1 of each period.

24-hour U-Na and U-K

For Na and K and the Na/K ratio, the baseline will be the value at Day -1 in each period.

CCI [Redacted]

[Redacted]

[Redacted]

[Redacted]

[Redacted]

[Redacted]

[Redacted]

[Redacted]

[Redacted]

Safety

ECG and vital signs

For ECG and vital signs, the baseline will be the pre-dose assessment at Day 1 in each period. If this value is missing the value closest in time prior to Day 1 within the same visit (or at Screening, in the case of period 1) will be the baseline for such a period.

Clinical chemistry/haematology/urinalysis

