4.12.2 Pharmacodynamics

All the models presented in this section will be analysed with unstructured covariance structure used for the within-participant errors. In the case of a model which does not converge, the analysis will be performed with a Toeplitz covariance structure and, in case of non-convergence, it will be performed with a compound symmetry structure.

Primary endpoint

The primary endpoint is the change in glucose AUC(0-4) and will be summarised by timepoint (baseline and Day 4) and by each cohort. The comparison of the change in glucose AUC(0-4) (where change from baseline in glucose AUC is assumed to be normally distributed) between the two treatments administered within each cohort after a standardised MMTT will be performed by means of two linear mixed effects models, with an unstructured covariance structure, with treatment, period and sequence as fixed effects, participant within sequence as random effect and baseline as covariate.

Two models will be run separately for each cohort:

1. In the first model, the dependent variable will be the change from baseline in AUC(0-4) whereas the AUC(0-4) on Day -1 will be included as a covariate. The treatment effects will be estimated by the Least Square means (LS means) and their 95% CIs and the difference between the two treatments by the difference in LS means with its 95% CI.

2. The second model will involve the following three steps:

a) Log-transformation of the AUC(0-4):

First, the AUC(0-4) in Day -1 and the AUC(0-4) in Day 4 will be log-transformed. The log-transformed AUC(0-4) in Day -1 will then be subtracted from the log-transformed AUC(0-4) in Day 4 to calculate the change in AUC (0-4) in log units.

b) Execution of the model:

The model will include the change in AUC (0-4) in log units as a dependent variable and the log-transformed AUC(0-4) in Day -1 as covariate.

c) Back-transformation of the results from the model:

The results from the execution of the model will be back transformed to the original scale after an exponentiation of the means and CIs estimated by the model to obtain the percentage geometric LS means of the treatments and their percentage SEs. The LS mean difference and its CI between the two treatments will also be back-transformed to yield the percentage geometric mean ratio between the two treatments with its 95% CI at Day 4.

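### Urinary sodium and potassium are analysed as concentrations although the objective and the protocol's statistics section call for 24-hour excretion, so a treatment effect on urine volume would enter both separate comparisons

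*SAP*

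**What the plan says.** Two quantities appear under the same heading.

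Excretion:
- The objective in protocol Table 2, repeated in SAP section 2, is "To determine the effect of AZD9567 on U-Na and U-K excretion compared to prednisolone".
- Protocol section 9.4.2.2 names as the variable to be analysed "24-hour U-Na and U-K excretion and the ratio between them". The statistical methods in the synopsis also say excretion.

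Concentration:
- The endpoint set beside that objective in both documents is "24-hour sodium and potassium concentration".
- Protocol section 8.2.3 says that "the concentration of sodium and potassium in urine will be measured over 24 hours". SAP section 3.2.1 agrees: "sodium and potassium concentrations in urine will be measured over 24 hours".
- SAP section 4.12.2 gives the analysis: "The 24-hour Na and K concentration and its ratio (Na/K) in urine will be analysed as the primary endpoint".

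On baseline, SAP section 4.8 says: "For Na and K and the Na/K ratio, the baseline will be the value at Day -1 in each period". The model carried over from the primary endpoint has "treatment, period and sequence as fixed effects, participant within sequence as random effect and baseline as covariate". It has no term for urine volume or creatinine. SAP section 4.15 records one change from the protocol, a time term in the repeated measures model, and does not mention the urinary endpoint.

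**The concern.** Excretion answers the question in the objective: how much sodium and potassium leaves the body in a day on each treatment. Concentration also depends on how much water leaves with them. If a treatment alters urine volume, the concentration moves even when the excreted amount does not, and a real change in amount can be hidden.

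Taking the change from Day -1 within each participant removes stable differences in volume between people. It does not remove a change in volume that the treatment itself causes. Such a change cannot be ruled out here. The treatments are expected to differ in their effect on glucose, and protocol Table 1 lists fluid and electrolyte disturbance and salt and water retention among the risks considered. At stake is the reading of two secondary results, U-Na and U-K taken separately.

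**Working it through.** The documents give no effect size, SD or power for this endpoint, so there is no planned figure to reproduce. The check is an identity plus assumed volume ratios.

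**Identity.** Concentration = excretion / volume. For the ratio of one treatment to the other:

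concentration ratio = excretion ratio / volume ratio

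The second model in SAP section 4.12.2 uses the log change from Day -1. On that scale:

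effect on log concentration = effect on log excretion − effect on log volume

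The SAP reports (exp(estimate) − 1) × 100, so a volume effect passes straight into the reported percentage. For example, with equal excretion and a volume ratio of 1.10, the estimate is −ln(1.10) = −0.0953 and the reported figure is (exp(−0.0953) − 1) × 100 = −9.1%.

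**Equal excretion (ratio 1.00), assumed volume ratios:**

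| Volume ratio | Concentration ratio | Change in concentration |
|---|---|---|
| 0.80 | 1/0.80 = 1.25 | +25% |
| 1.10 | 1/1.10 = 0.909 | −9.1% |
| 1.20 | 1/1.20 = 0.833 | −16.7% |
| 1.25 | 1/1.25 = 0.80 | −20% |

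Analysed as an amount, each row would give a ratio of 1.00.

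**Masking.** If excretion and volume are both 20% lower on one treatment, the concentration ratio is 0.80/0.80 = 1.00. A true fall in excretion would not show.

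**Na/K.** (Na amount / volume) / (K amount / volume) = Na amount / K amount. Volume cancels, so the ratio is the same on either definition. It cannot show whether both ions rose or fell together, so it does not replace excretion.

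**Illustration of the consequence for a test.** Take n = 24 (Cohort 1 completers), two-sided 0.05, a normal approximation, and an assumed SD of the within-participant log difference of 0.3 to 0.6. With equal excretion and a volume ratio of 1.2:
- At SD 0.3, the standard error is 0.3/√24 = 0.0612, and ln(1.2)/0.0612 = 2.98. The chance of a significant concentration difference is Φ(2.98 − 1.96), about 85%.
- At SD 0.6, the standard error is 0.6/√24 = 0.1225, and ln(1.2)/0.1225 = 1.49. The chance is about 32%.

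At a volume ratio of 1.1 the corresponding figures are 34% and 12%. The test would be correct about concentration; the error lies in reading it as excretion. Both the SD and the volume ratio are assumed, so these figures show the mechanism and do not estimate the risk in this trial.

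**The case against.** The strongest reply is that the mismatch may be only one of wording. Urine is collected over 24 hours, and the protocol's statistics text calls the result excretion. A 24-hour concentration may therefore be loose language for a 24-hour amount. Collection is governed by a laboratory manual that is not among the documents, and volume may be recorded there or in the eCRF. The SAP also agrees with the protocol's own endpoint column and section 8.2.3, so the conflict begins inside the protocol. All of this is fair. It means one cannot say that volume was not collected. It does not settle what is analysed: the SAP says concentration, and no visible text derives an amount.

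A reader might go further and infer three things that the documents do not support.

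- **A known direction of bias.** One might argue that higher glucose on prednisolone enlarges urine volume, dilutes sodium and imitates retention. The documents give no urine volume or urinary glucose data by treatment. Table 1 also names salt and water retention, which could reduce volume and raise concentration. The direction is open.
- **A confounded mineralocorticoid comparison as a whole.** Na/K is free of volume and uses the same model. SAP section 4.11.3 separately models Na, K and Na/K under the clinical laboratory evaluation, and protocol Table 1 assigns mineralocorticoid monitoring to morning plasma markers. Only the separate U-Na and U-K results are exposed.
- **Urinary creatinine as a ready substitute for volume.** Creatinine is on the urinalysis panel. However, the SAP schedule puts urinalysis on Days -2, 1 and 4 of each period, while the 24-hour collections are on Days -1 and 3.

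**Conclusion.** The concern holds for U-Na and U-K taken separately. The inconsistency needs no assumption: the objective and the protocol's statistics text target excretion, the SAP analyses concentration, and section 4.15 does not declare the difference. The size depends on a volume effect that the documents do not give. Across the assumed range, from 20% smaller to 25% larger volume, concentration would shift by +25% to −20% with no change in excretion. If the laboratory already reports amount per 24 hours, the error is in the wording alone, but the passages must still be reconciled. This is a secondary endpoint in a Phase 2a study; the primary glucose analysis and the Na/K ratio are not affected.

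**What to change.** - In SAP sections 3.2.1, 4.8 and 4.12.2, define U-Na and U-K as 24-hour excretion: mmol/24 h = concentration (mmol/L) × total collected volume (L), for the Day -1 and Day 3 collections of each period.
- Analyse the change in excretion with the planned cross-over model and keep Na/K as planned. Show concentration and volume descriptively by treatment. Bring the endpoint wording in both documents into line with the objective.
- Use a ratio to creatinine only if creatinine was assayed in the same 24-hour collection.
- If volume was not recorded, limit the conclusion to concentration and Na/K, and list the departure from protocol section 9.4.2.2 in SAP section 4.15.

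The cost is SAP wording and one derived variable, since the collections are already scheduled. The real requirement is that 24-hour volume was captured. The protocol estimated last participant completion for May 2021 and SAP version 3.0 is dated October 2021, so if those dates held, a volume that was not measured could not be supplied later.
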